9.5.1.4.5. Dilated Fundus Exam (DFE)

Dilated ophthalmoscopy will be performed in each eye with an indirect ophthalmoscope to evaluate any posterior segment abnormalities. When possible, for consistency purposes, the same lens should be used for all assessments throughout the study. Clinically significant abnormal findings will be reported on the eCRF.

9.5.1.4.6. Post-Injection Assessment

Post-injection assessment is to be performed within 15 minutes after the injection checking for finger counts or hand motion and measuring IOP using site specific SOPs; if needed, the patient can be requested to do additional examinations (i.e., additional IOP or ophthalmoscopy), per discretion of the Investigator prior to completing the study visit.

In addition, a next-day post-injection on-site safety visit will be conducted in all patients which will comprise of assessments such as adverse events, BCVA, IOP, slit lamp biomicroscopy and dilated fundus exam.

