SRC	Safety Review Committee
ST	The Plateau Phase of the Action Potential
TEAE	Treatment emergent adverse event
VEGF	Vascular Endothelial Growth Factor

WBC	White blood cell count
WHODrug	World Health Organization Drug Dictionary

PROTOCOL SYNOPSIS

Title: A Multicenter, Open-Labeled, Phase 2a Study Evaluating the Safety, Tolerability, and Efficacy of Intravitreal AG-73305 in Patients with Diabetic Macular Edema.

Study Objectives:

- ◆ Evaluate the safety, tolerability, duration of effect, systemic pharmacokinetic (PK) and immunogenicity profile of ascending doses of AG-73305 administered by intravitreal (IVT) injection in patients with diabetic macular edema (DME).
- ◆ Evaluate pharmacodynamic endpoints (e.g., best-corrected visual acuity [BCVA], spectral domain optical coherence tomography [SD-OCT] and OCT-angiography [OCT-A]).
- ◆ Determine the maximum tolerated dose or the highest administered dose for evaluation in future studies.

Study Description: This is a multi-centered, open-labeled, single ascending-dose-cohort study with a sentinel patient at each dose level. Cohort management will be overseen by a Safety Review Committee (SRC). The following hypotheses will be evaluated:

- ◆ AG-73305 has an acceptable safety profile, as measured by the incidence and severity of adverse events (AEs).
- ◆ At least 1 dose of AG-73305 demonstrates some clinical beneficial effects as measured by SD-OCT, BCVA and OCT-A findings.

Response Measures:

Safety assessments:

- Adverse Events (AEs)
- ETDRS BCVA
- Intraocular pressure (IOP)
- Slit lamp biomicroscopy
- Dilated fundus exam (DFE)
- Crystalline lens assessment using AREDS scale
- Post-injection assessment
- Laboratory evaluation (hematology, serum chemistry and urinalysis)
- Electrocardiogram (ECG)
- Vital signs
- Physical examination
- Pregnancy test

Efficacy assessments:

- Improvements in ETDRS BCVA
- SD-OCT (Heidelberg Spectralis, dense scan) as measured by Central Reading Center (CRC)
 - Central subfield thickness (CST)
 - Ellipsoid zone (EZ)
 - External limiting membrane (ELM)
 - Intraretinal and subretinal fluid
 - Posterior vitreous detachment
- OCT-A as measured by CRC
 - Foveal avascular zone (FAZ)
 - Foveal capillary density (CD) (superficial and deep capillary plexuses)
- Diabetic retinopathy severity score (DRSS) assessed via color fundus photography
- Time to rescue medication

Pharmacokinetics: Plasma concentrations of AG-73305.

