2. ETDRS BCVA
3. Intraocular pressure (IOP)
4. Slit lamp biomicroscopy, including crystalline lens assessment using AREDS scale
5. Dilated fundus exam (DFE)
6. Post-injection assessment
7. Laboratory evaluation (hematology, serum chemistry and urinalysis)
8. Electrocardiogram (ECG)
9. Vital signs
10. Pregnancy test

The FAS will be used for all safety analyses. All data will be summarized as observed and no data imputation will be performed. No statistical treatment group comparisons will be performed, unless otherwise specified. Analyses will be presented by cohort and by study eye and non-study eye, if applicable.

Results from the physical examination performed at Screening will be presented in a listing.

All safety data will be censored (set to missing) on or after the earliest instance of rescue therapy when summarized in tables. All data will be presented in listings. This will impact the definition of TEAE.

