9.7.1.6.1. Adverse Events

AEs are coded using MedDRA Version 25.0. Treatment-emergent adverse events (TEAE) are defined as events that start on or after the administration of study medication and up to the earliest instance of rescue therapy. Pretreatment adverse events are events that begin prior to administration of study medication. Ocular AEs are defined as those events for which an eye has been specified (OD, OS, or OU).

Ocular and non-ocular treatment-emergent AEs will be summarized separately. Ocular AEs will be presented by study eye and non-study eye and overall (OU) if an event occurs in either eye.

In all summaries of AEs, percentages are calculated based on the number of patients in each treatment group of the Safety Analysis Set.

Overall summaries of AEs by treatment will include:

- the number of AEs and SAEs reported;
- the number and percentage of patients who experienced any AE;

- the number and percentage of patients who experienced any serious adverse event (SAE) and the reason for seriousness;
- the number and percentage of patients with any AE by worst severity and worst relationship.

The overall summaries of TEAEs will also include the number and percentage of patients with any TEAEs leading to study termination.

Summaries of the frequency and percentage of patients with AEs by SOC and preferred term by treatment group will include:

- All AEs by SOC and preferred term;
- All AEs by SOC, preferred term, and maximum severity;
- All AEs by SOC, preferred term, and maximum relationship.

System organ class (SOC) will be sorted alphabetically, and preferred term (PT) within each SOC will be sorted by overall descending order of frequency according to the following rules in order:

1. Descending frequency within AG-73305, 0.5 mg;
2. Descending frequency within AG-73305, 1 mg;
3. Descending frequency within AG-73305, 2 mg;
4. Descending frequency within AG-73305, 4 mg;
5. PT in alphabetical order.

Patients are counted only once for each SOC and PT. In summaries of maximum severity and maximum relationship, patients with multiple occurrences of events will only be counted once at the maximum severity/relationship per SOC and PT.

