9.8. CHANGES IN THE CONDUCT OF THE STUDY OR PLANNED ANALYSES

9.8.1. Protocol Amendments

-

Amendment 1 made the following changes:

- Sponsor address;
- Exclusion criteria 19f.

Amendment 2 made the following changes:

- The additional collection of safety assessments the next day after dosing;
- The addition of a 24-hour post-dose PK sample for Cohorts 3 and 4;
- Clarification on timing and specificity of some assessments.

Amendment 3 made the following changes:

- Changed the dose of Cohort 4 to 4mg (0.1 mL);
- Updated CST trigger for rescue medication;
- Added 14-day extension to screening window;
- Updated safety data and margin;
- Updated inclusion criteria;
- Updated schedule of activities;
- Updated prohibited medications;
- Updated storage conditions.

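### If any lower-dose patients were dosed before Amendment 2 added the next-day assessments, cumulative adverse-event incidence by dose rests on unequal early examination, and the SAP has no rule for this

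*SAP*

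**What the plan says.** SAP 9.5.1.4.6 describes a 15-minute post-injection check (gross vision and IOP, with ophthalmoscopy at the investigator's discretion). It then says that "a next-day post-injection on-site safety visit will be conducted in all patients", covering AEs, BCVA, IOP, slit lamp and dilated fundus examination. The schedules in protocol 1.3 and SAP Appendix I show the Day 2 column without a cohort limit.

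SAP 9.8.1 lists two items together under Amendment 2: "The additional collection of safety assessments the next day after dosing" and "The addition of a 24-hour post-dose PK sample for Cohorts 3 and 4". Amendment 3 later changed the Cohort 4 dose. No amendment date, dosing date or count of patients per protocol version is given.

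The synopsis describes the order of dosing: "This is a multi-centered, open-labeled, single ascending-dose-cohort study with a sentinel patient at each dose level". There is no randomization.

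On safety, SAP 9.7.1.6 says "Analyses will be presented by cohort and by study eye and non-study eye, if applicable" and "All data will be summarized as observed and no data imputation will be performed". SAP 9.7.1.6.1 reports "the number and percentage of patients who experienced any AE", with all patients in the dose group as denominator. SAP 9.7.1.6.2 and 9.7.1.6.3 count patients with BCVA losses of at least 5, 10 and 15 letters and IOP rises of at least 10 mmHg; those sentences name no visit.

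**The concern.** For a patient dosed without the Day 2 assessments, the first slit-lamp and dilated examination on the current schedule after the post-injection check is Week 1, Day 8 ± 2. A symptom-free sign that clears before then would go unrecorded. The same sign in a patient with a Day 2 visit becomes a treatment-emergent AE (TEAE). An extra visit also gives one more chance to cross a BCVA or IOP threshold if those counts mean ever during the study.

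If presence of the visit follows dose, a table of cumulative incidence by cohort mixes dose with intensity of examination, and the distortion runs toward an apparent dose-toxicity trend. Tolerability of ascending doses is among the first-listed objectives. With 3 to 8 patients per cohort (SAP 9.7.2), one additional case moves incidence by 1/8 = 12.5 to 1/3 = 33 percentage points. The SAP, which already lists Amendment 3, says nothing about patients treated under the earlier schedule.

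**Working it through.** **Who may lack the visit.** Three facts make it plausible that some or all of Cohorts 1-2 were dosed before Amendment 2:
- The 24-hour PK sample was added only for Cohorts 3 and 4.
- Cohorts 1 and 2 keep a different plasma schedule, with a 1-hour sample and no 24-hour sample (SAP 9.5.1.5.1).
- Amendment 3 was still changing the Cohort 4 dose.

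This is inference, and the PK difference could have another reason.

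**Which outputs are exposed.**

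| Output | Denominator or timing | Exposed? |
|---|---|---|
| AE/TEAE incidence (9.7.1.6.1) | All patients in dose group, cumulative | Yes |
| BCVA-loss and IOP-rise counts (9.7.1.6.2, 9.7.1.6.3) | Visit not named | Only if read as ever |
| Observed and change in BCVA and IOP | By scheduled visit | Largely not |
| Slit lamp and fundus (9.7.1.6.4, 9.7.1.6.5) | Patients at that visit, or with paired values | Largely not |
| Attendance (9.7.1.2) | By cohort and visit | Would reveal a missing Day 2 |

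**The plan's own figure.** SAP Table 2 gives the chance of at least one case as 1 − (1 − p)^n. For n = 6 and p = 0.2, this is 1 − 0.8^6 = 0.738, as printed. All 24 cells reproduce, with a largest difference of 0.0005. No figure in the plan is disputed.

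**Illustration.** All of these are assumptions, apart from the choice of 6 per cohort, which follows from about 25 patients in 4 cohorts:
- The true rate p of a Day 2 finding is the same at every dose.
- There are 6 patients per cohort, so 12 in Cohorts 1-2 and 12 in Cohorts 3-4.
- Cohorts 1-2 have no Day 2 visit and Cohorts 3-4 all have it.
- A share w of findings is still detected or reported at Week 1.

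The expected counts are 12pw at the lower doses and 12p at the higher doses. The probabilities come from two independent binomials, Bin(12, pw) and Bin(12, p).

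| p | w | Expected, lower | Expected, higher | P(higher doses show more) | P(lower doses show more) |
|---|---|---|---|---|---|
| 0.1 | 0 | 0 | 1.2 | 0.718 | 0 |
| 0.1 | 0.5 | 0.6 | 1.2 | 0.516 | 0.179 |
| 0.2 | 0 | 0 | 2.4 | 0.931 | 0 |
| 0.2 | 0.25 | 0.6 | 2.4 | 0.798 | 0.062 |
| 0.2 | 0.5 | 1.2 | 2.4 | 0.657 | 0.158 |
| 0.2 | 1 | 2.4 | 2.4 | 0.398 | 0.398 |
| 0.4 | 0.25 | 1.2 | 4.8 | 0.941 | 0.019 |

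The w = 1 row is equal ascertainment: the two directions balance and there is no artificial trend. At p = 0.2 and w = 0.25, a gap of at least 3 patients in favour of the higher doses occurs in 32% of trials, against 10% with equal ascertainment.

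In a single cohort of 6 at p = 0.2, the chance of at least one detected case is 0.738 with the visit. Without it, at w = 0.25, the detected rate is 0.2 × 0.25 = 0.05 and the chance falls to 1 − 0.95^6 = 0.265.

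**Sensitivity of the most striking pattern.** The chance of at least one case in Cohorts 3-4 and none in Cohorts 1-2, at p = 0.2, is:
- w = 0: 1 − 0.8^12 = 0.931.
- w = 0.25: 0.931 × 0.95^12 = 0.50.
- w = 0.5: 0.931 × 0.90^12 = 0.26.
- w = 0, with half of Cohorts 1-2 having the visit: 0.931 × 0.8^6 = 0.24.

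**The case against.** The key fact is absent: nothing dates Amendment 2 or any dosing. A reader might infer that only the higher-dose cohorts were examined on Day 2. The documents do not support that as fact, and if every patient was dosed after the amendment there is no bias. The amendment entry speaks of additional collection of assessments, so some earlier next-day contact cannot be excluded. This stands, and the point must be conditional.

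The sentence in 9.5.1.4.6 also agrees with both current schedules, and a difference between an amendment log and current text is not an error. That stands too. The log serves here only as evidence that the schedule changed; the gap is the missing analysis rule.

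By-visit tables and the attendance table already handle or expose a missing Day 2. This narrows the exposure to cumulative AE incidence and an ever reading of the threshold counts.

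A reader might also infer that the maximum tolerated dose will be chosen from these tables, or that a spurious trend is near certain. No section says the former: a Safety Review Committee oversees the cohorts, the sample-size rationale concerns DLTs and SAEs, and 9.7.1.6 plans no statistical group comparisons unless otherwise specified. As for the latter, 93% is a worst case in which no Cohort 1-2 patient had the visit and no finding survives to Week 1.

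Finally, dropping Day 2 events would discard real acute-tolerability data. That is a fair objection to replacing the tables, but not to adding one beside them.

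**Conclusion.** The concern holds as a conditional one. The schedule changed at Amendment 2, any earlier-dosed patients would belong to the lower doses, and the SAP has no rule for them. If there are such patients, cumulative AE/TEAE incidence by cohort can mimic a dose trend for transient, symptom-free signs, as can the BCVA-loss and IOP-rise counts if taken over the whole study. Symptomatic events can still be reported at Week 1.

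The size cannot be fixed from the documents. The illustrated 0.6/12 against 2.4/12, and about 80% against 40% of trials with more cases at the higher doses, rest on the assumed 20% rate, the quarter still caught at Week 1 and the assumed split of cohorts. The effect shrinks as more lower-dose patients had the visit or more findings last to Week 1. This is a cheap improvement to the reporting plan, not a flaw in the trial's design.

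**What to change.** 1. Derive a patient-level flag for whether the Day 2 visit was in force in the protocol version at dosing, and show the number per cohort. If all patients had it, the matter closes.
2. If any cohort has patients without it, amend SAP 9.5.1.4.6 to limit the statement to patients dosed under Amendment 2 or later.
3. In that case, also add to 9.7.1.6 a supplementary by-cohort summary of TEAEs and of the BCVA and IOP threshold counts, leaving out findings first detected only at the Day 2 examination. Place it beside the unchanged all-visits tables. If the manner of detection is not recorded, one workable rule, applied identically in every cohort, is to leave out events that began by the Day 2 visit and ended before Week 1.
4. State in 9.7.1.6.2 and 9.7.1.6.3 whether the threshold counts are per visit or ever during the study.
5. Footnote the all-visits AE table: early findings should not be compared across doses from that table alone.

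The cost is one derived variable, one extra summary and some wording; no new data collection is needed. The downside is that the supplementary summary omits real Day 2 events, so it must not replace the all-visits tables.

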9.5.1.4.7. Laboratory Evaluation (Hematology, Serum Chemistry and Urinalysis)

Hematology. Includes hematocrit, hemoglobin, mean corpuscular hemoglobin, mean corpuscular hemoglobin concentration, mean corpuscular volume, platelets, red blood cell (RBC) count, RBC morphology, total white blood cell (WBC) count, and differential (neutrophils, bands, lymphocytes, monocytes, basophils, and eosinophils).

Non-fasting serum chemistry. Includes albumin, alkaline phosphatase, Alanine amino Transferase (ALT), Aspartate amino Transferase (AST), bicarbonate, calcium, chloride, creatinine, direct bilirubin, gamma-glutamyl transferase, indirect bilirubin, magnesium, non-fasting glucose, (HbA1C), phosphorous, potassium, sodium, total bilirubin, total cholesterol, total protein, urea nitrogen, and uric acid.

Urinalysis. Includes clarity, color, bilirubin, creatinine, blood, glucose, ketones, leukocyte esterase, nitrite, pH, protein, specific gravity, urobilinogen, microscopic sediment (WBCs, RBCs, casts, bacteria, crystals, and epithelial cells), and screen for drug use.

Approximately 13.5 mL of blood will be drawn for clinical laboratory evaluations at the required visits. A qualified central laboratory will receive all blood and urine samples from the site(s) and will analyze and report the results. Data will be transferred to Allgenesis or their designee on a periodic basis throughout the duration of the study.

9.5.1.4.8. Electrocardiogram (ECG)

Electrocardiograms will be obtained using a 12-lead standard equipment. The investigator will be responsible for the initial review of the ECG to assess whether the ECG is within the reference limits. All ECGs will be sent to a central reader for interpretation, including confirmation of eligibility and ongoing safety assessments, and assessed for the following measures: P wave, QRS complex, U wave, QRS duration, QT interval, T wave, ST segment, RR interval, PR interval, and qualitative results. Blood draws, vital signs, and other procedures should be delayed until after each ECG.

9.5.1.4.9. Vital Signs

Systolic and diastolic blood pressure (mmHg), heart rate (BPM), body temperature (°F) and respiratory rate (breaths per minute) will be measured after patients have been at rest (seated) for at least 5 minutes.

9.5.1.4.10. Pregnancy Test

Pregnancy testing will be performed using a human chorionic gonadotropin pregnancy urine dipstick test for female patients of childbearing potential only.

9.5.1.5. Other Assessments

9.5.1.5.1. Pharmacokinetics

In a subset of at least 2-4 patients per study group (at selected study sites), blood samples (approximately 10 mL per sample) will be collected for monitoring the plasma concentrations of AG-73305. In cohorts 1 and 2 on plasma monitoring samples will be collected on Day 1 at pre-dose and at 1, 3, and 8 after the intravitreal injection, and at the Week 1 and 4 visits. In cohorts 3 and 4, samples will be collected on Day 1 at pre-dose and at 3, 8 and 24 hours after the intravitreal injection, and at the Week 1 and 4 visits. Plasma drug concentrations will be measured using a validated enzyme-linked immunosorbent assay, with a target lower limit of quantitation of ~1 ng/mL. Allgenesis shall have full ownership rights to any biological samples derived from the study.

9.5.1.5.2. Immunogenicity

Blood samples (approximately 20 mL per sample) will be collected for the assessment of anti-drug antibodies towards AG-73305 at pre-dose, Week 1, 4, 8 and 24.

9.5.2. Appropriateness of Measurements

All assessments used in this study are widely used and generally recognized as reliable, accurate, and relevant.

9.5.3. Primary Efficacy Variable(s)

The key efficacy measure is best-corrected visual acuity score of the study eye using the ETDRS as assessed by certified Investigator or designee. The endpoint is the change from baseline in overall BCVA score at Week 4.

9.5.4. Drug Concentration Measurements

The measurement of plasma drug concentration will be conducted at B2S Life Sciences and transferred to Lexitas. Plasma drug concentrations will be measured using a validated enzyme-linked immunosorbent assay, with a target lower limit of quantitation of ~1 ng/mL.

9.6. DATA QUALITY ASSURANCE

Each clinical site will perform internal quality management of study conduct, data and biological specimen collection, documentation, and completion.

Quality control (QC) procedures will be implemented beginning with the data entry system and data QC checks that will be run on the database will be generated. Any missing data or data anomalies will be communicated to the site(s) for clarification/resolution.

Following written Standard Operating Procedures, the monitors will verify that the clinical trial is conducted, and data are generated, and biological specimens are collected, documented (recorded), and reported in compliance with the protocol, ICH-GCP, and applicable regulatory requirements (e.g., GLP, Good Manufacturing Practice).

The investigational site will provide direct access to all trial-related sites, source data/documents, and reports for the purpose of monitoring and auditing by the sponsor, and inspection by local and regulatory authorities.

9.6.1. Training and Education of Investigators and Study Site Personnel

An Investigator Meeting will be held before study initiation and attended by the Investigators and/or Sub-Investigators from each study site, study coordinators from each study site, if possible, and personnel from the sponsor and the Contract Research Organization (Lexitas Pharma Services, Inc., hereafter referred to as Lexitas). The purpose of this meeting is to train and instruct the Investigators and the study coordinators on the proper conduct of the clinical trial and ensure that all patients are aware of their obligations set out by the protocol, ICH guidelines, GCP guidelines, and other applicable regulatory requirements.

9.6.2. Monitoring of Study Sites

Clinical site monitoring is conducted to ensure that the rights and well-being of the trial patients are protected, that the reported trial data are accurate, complete, and verifiable, and that the conduct of the trial is in compliance with the currently approved protocol/amendment(s), with ICH Good Clinical Practice (GCP), and with applicable regulatory requirement(s).

- A representative of Allgenesis will monitor the study on a periodic basis. The determination of the extent and nature of monitoring will be based on considerations, such as the objective, purpose, design, complexity, masking, size, and endpoints of the study.
- Authorized representatives of Allgenesis or regulatory authority representatives will conduct on-site visits to review, audit, and copy study-related documents. These representatives will meet with the investigator(s) and appropriate staff at mutually convenient times to discuss study-related data and questions.

9.6.3. Data Entry and Verification of Database Used for Analysis and Reporting

Data collection is the responsibility of the clinical trial staff at the site under the supervision of the site's Investigator. The Investigator is responsible for ensuring the accuracy, completeness, legibility, and timeliness of the data reported.

Lexitas will review the eCRFs entered by investigational site staff for completeness and accuracy and instruct the investigational site staff to make any required corrections or additions. After data have been entered into the study database, a system of computerized data validation checks will be implemented and applied to the database. Queries will be sent to the investigational site and designated investigational site staff are required to respond to the query and edit data, as necessary. All changes to the study database will be documented.

It is the responsibility of the monitor to make certain that all data are completed on the eCRFs. At the end of each study period, the Investigator will sign and date the eCRF to attest to the authenticity of the collected data and coherence between the data in the eCRF and the data in the source documents.

Collection of SD-OCT, OCT-A, and color fundus imaging will be done at sites with the requisite equipment and certified by an independent imaging reading center. The grading of images will be completed by the reading center.

BCVA measures will be performed by qualified technicians who have recent or current certification to minimize bias. Appropriate and relevant documentation of certification of the technicians at each investigative site will be provided prior to screening any study patients.

